In addition, each PAP contains an internal SD (data storage) card that contains PAP usage data. In instances when the modem data are incomplete, the SD card data will be imported into the study's database on the Encore Anywhere website. The SD card data will be compared to the modem data to ensure that there are complete data for the entire 12-month follow-up period. The temporary removal of the SD card from the PAP machine will not impact the therapeutic benefits of PAP use nor its function. In a study conducted by our research group ([name], project #0015), we found subtle variation in the modem PAP use data across time, which was addressed by having an SD card download available at various timepoint in the study. SD card downloads at 3, 6, 9 and 12 months will insure the accuracy and completeness of the PAP use data. Both methods allow collection of PAP usage data with no additional burden to participants. We will use monthly PAP use as an outcome measurement.

All participants will continue to receive usual care from the SDC, including periodic telephone contact to monitor PAP adherence and follow-up physician visits. Participants will continue to be followed by the clinic at the conclusion of the study.

• Intervention process measures (ABC-SA and control)

Participants in both study groups will complete the following questionnaires at the end of the first treatment and final (sixth) treatment sessions. We have selected this approach since some measures cannot be completed until the individual has a basic understanding of the treatment program she will receive.

Acceptance and Action Questionnaire-II (AAQ-II):¹⁹ The AAQ-II is a 7-item questionnaire to assess experiential avoidance as conceptualized in ACT (higher scores suggest more avoidance). The AAQ-II has acceptable psychometric properties. In a recent study of 376 adults with depression or anxiety symptoms, *Study protocol* 8 *Version: 2/24/2021* using a unidimensional item response theory (IRT) model, the AAQ-II was found to be a unidimensional measure of experiential avoidance with satisfactory reliability. Key variable: AAQ-II total score.

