Dysfunctional Beliefs and Attitudes about Sleep – 10 item (DBAS-10):²⁰ The DBAS-10 is an abbreviated version of the original 28-item DBAS examining beliefs about the immediate and long-term negative consequences of insomnia as well as beliefs about the need for control over insomnia. This 10-item version has been shown to be well correlated (r=0.83) with the full scale and sensitive to cognitive changes resulting from cognitive-behavioral therapy for insomnia. Key variables: DBAS total score.

Sleep Hygiene Index (SHI)²¹ The 13-item sleep hygiene index is based on diagnostic criteria for inadequate sleep hygiene, and has superior reliability compared to other (typically longer) sleep hygiene questionnaires (Chronbach's α =0.66). This measure will be used to identify sleep hygiene related behaviors, including the use of alcohol, caffeine and tobacco within 4 hours of bedtime. Key variable: SHI total score.

Credibility/expectancy questionnaire (CEQ):²² The CEQ is a 6-item questionnaire used both at the beginning and end of treatment. This questionnaire will be administered at the end of the first treatment session and again at the end of the final treatment session in both groups. Since this measure cannot be used until the individual understands the type of treatment she will receive, it will not be assessed until after session 1 when information about the treatment is available. The post-treatment items will be administered at the end of the final treatment session 6). Differences in scores between the groups will be explored. Key variable: CEQ total scores at the beginning and end of treatment.

Treatment sessions will also be audio recorded and one of the study investigators will listen to and rate sessions using a Fidelity Monitoring Form to assess adherence to the intervention content and competency of the study interventionist.

COVID-19 amendment for intervention /control sessions

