Randomized participants will be mailed the session materials for all 5 weeks of the intervention/control conditions prior to the first session. They will also be provided with postage-paid return envelopes to mail the sleep diaries and process measure questionnaires to the research office. Interventionists will meet weekly with participants via video platform. The content of the sessions will be identical to the in-person sessions and the interventionist will follow the same protocols as described above. PAP devices will be mailed to participants following session 2. (GLAHS Sleep Medicine clinics are currently mailing PAP devices to patients and providing set-up instructions using VVC.)

		ABC-SA Program	Control Program							
Week	Title Components/Topics		Title	Components/Topics						
Week 1	Don't take out the trash: Understanding SA and PAP	 Metaphor: Trash can for unwanted feelings What is SA? How does PAP work? How will it impact my sleep? What is important to me/how can PAP fit into my life? De-fusion from thoughts about PAP Sleep education/healthy sleep habits Introduce sleep dairy 	Understanding sleep	General information about sleep in adults; sleep stages, circadian rhythms						
Week 2	Putting the day to rest: Getting ready for PAP	 Metaphor: Wearing glasses Sleep apnea and relationships with others Review homework/sleep diary Develop sleep schedule with specific bedtime/rise time. Develop bedtime routine Preparing for PAP: take steps to get ready 	What is sleep apnea?	General information about sleep apnea; Basics of PAP use (usual care)						
		PAP therapy begins								
Week 3	Going swimming: Getting started with PAP	 Metaphor: Jumping into cold water Review homework/sleep diary Practice with equipment and mask Adjustment of sleep schedule Revise bedtime routine to include PAP setup How will PAP use fit into your life? Introduce sleep diary with PAP use monitoring 	What is PAP?	Basic information about sleep disordered breathing; introduction to PAP equipment						
Week 4	What was it like to try something new?	 Metaphor: Tasting new foods Review homework/sleep diary, review PAP usage data Troubleshoot equipment challenges Informed choices about PAP use: moods and feelings Adjust bedtime/rise time (if indicated) 	Good sleep hygiene I	Sleep hygiene: sleep environment considerations						

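### AAQ-II, DBAS-10 and SHI have no pre-randomisation score; the first is taken after session 1, so change from it may understate an early ABC-SA effect

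*Combined protocol and SAP*

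**What the plan says.** Under Intervention process measures, the protocol lists the AAQ-II, DBAS-10, SHI and CEQ and fixes their timing: "Participants in both study groups will complete the following questionnaires at the end of the first treatment and final (sixth) treatment sessions". The reason given is that "some measures cannot be completed until the individual has a basic understanding of the treatment program she will receive". That reason is spelled out for one instrument, the CEQ, of which the text says that "it will not be assessed until after session 1 when information about the treatment is available".

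The other three are described as measures of the woman herself. The AAQ-II covers experiential avoidance. The DBAS-10 covers beliefs about insomnia and is called "sensitive to cognitive changes resulting from cognitive-behavioral therapy for insomnia". Of the SHI the protocol says: "This measure will be used to identify sleep hygiene related behaviors, including the use of alcohol, caffeine and tobacco within 4 hours of bedtime".

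Table 5, the schedule of measures, lists none of the four at any time point. Table 4 gives the Week 1 content. For ABC-SA it includes a metaphor about unwanted feelings, "De-fusion from thoughts about PAP" and "Sleep education/healthy sleep habits". For control it is general facts about adult sleep, and sleep hygiene comes only in Weeks 4 and 5.

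The only analysis sentence for process measures stands in the CEQ paragraph and says that between-group differences will be explored.

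**The concern.** A baseline is useful because treatment cannot have affected it. Here the first score on three scales follows both randomisation and a session whose content differs by arm. Any early effect of ABC-SA would be counted as part of the starting value, and later change would then look smaller than the effect of the whole programme.

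What is at stake is the account of how ABC-SA works. Its stated focus is psychological flexibility, and the AAQ-II is the one scheduled instrument described as measuring an ACT construct. Without a pre-randomisation score, balance between arms on these scales cannot be checked, and the baseline-adjusted ANCOVA that the plan prefers for Aims 2 and 3 is not available for them.

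**Working it through.** **Does the stated reason cover each scale?**

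| Scale | What it asks about | Needs knowledge of the programme? | ABC-SA session 1 content on it |
|---|---|---|---|
| AAQ-II | experiential avoidance | no | direct: unwanted-feelings metaphor, de-fusion (about PAP) |
| DBAS-10 | beliefs about insomnia | no | indirect: sleep education |
| SHI | sleep-hygiene behaviours | no | direct: sleep habits, though behaviour has had little time to change |
| CEQ | credibility and expectancy of the treatment | yes | not applicable |

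The reason fits the CEQ alone. Under the COVID-19 amendment, session materials are mailed before the first session, so exposure may come even earlier.

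**What the timing does to an estimate.** The plan gives no figure for these scales, so there is none to reproduce. Let D be the between-arm difference at session 6 in SD units, f the share of D already present at the end of session 1, and r the correlation between the two scores, with equal SDs.

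- Difference in change from session 1: D − fD = D(1 − f), SD √(2(1 − r)).
- ANCOVA on the session 1 score (slope r): D − r·fD = D(1 − rf), SD √(1 − r²).
- Session 6 score by arm, unadjusted: D, SD 1.

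*Check of the setup.* The Aim 2 detectable effects come from (1.960 + 0.842) × √(2/36) × √(1 − r²). For r = .62, .35 and .24 this gives 0.518, 0.619 and 0.641, against .52, .62 and .64 in Table 6.

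*Illustration.* Assumed: D = 0.62 and r = .35 (borrowed from the PSQI row of Table 6), 36 per group, two-sided alpha .05. None of these is given for the three scales. The row f = 0 is also what a true pre-randomisation score with the same r would give.

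| f | Change: estimate (power) | ANCOVA: estimate (power) | Session 6 only |
|---|---|---|---|
| 0 | 0.62 (64%) | 0.62 (80%) | 0.62 (75%) |
| 0.10 | 0.56 (55%) | 0.60 (77%) | 0.62 (75%) |
| 0.25 | 0.47 (41%) | 0.57 (73%) | 0.62 (75%) |
| 0.50 | 0.31 (21%) | 0.51 (64%) | 0.62 (75%) |
| −0.20 | 0.74 (79%) | 0.66 (85%) | 0.62 (75%) |

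At f = 0.25, ANCOVA loses 0.35 × 0.25 = 9% of D. With r = .62 (the actigraphy row of Table 6) it loses 0.62 × 0.25 = 16%, an estimate of 0.52. In the same setting, adjusting for an uncontaminated baseline gives 80% power at r = .35 and 92% at r = .62, against 75% unadjusted.

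**The case against.** A reader might infer that change on these scales is biased towards no effect as a matter of fact. The documents do not support that, for three reasons.

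- **No such analysis is planned.** There is no change-score, ANCOVA or mediation analysis of the AAQ-II, DBAS-10 or SHI. The ANCOVAs in the plan belong to Aims 2 and 3 and adjust for true baseline values. A comparison of session 6 scores by arm is not biased by the missing baseline.
- **The direction is conditional.** Attenuation needs f > 0. With f = 0 there is no bias, and with f < 0 it runs away from the null. Nothing in the documents estimates f.
- **An immediate effect is not equally likely on all scales.** It is plausible mainly for the AAQ-II, and even there the de-fusion work concerns PAP while the scale is general. The DBAS-10 link is indirect. SHI behaviours can hardly change within one session, although reporting of them may.

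It is also tempting to put a size on the loss by spreading the effect over the sessions. With f from 1/6 to 1/3, a d of .50 would show as .50 × 5/6 = .42 down to .50 × 2/3 = .33. That range is an assumption that leaves out zero, and it applies only to raw change. ANCOVA with r = .35 would give .47 to .44, and session 6 scores alone .50.

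These points limit the claim and all of them stand. They do not supply a reason for giving three scales late, and the session 6 comparison avoids bias only by giving up baseline adjustment. The plan itself values that adjustment in Aim 2 for its power and its control of baseline differences.

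**Conclusion.** The point holds as a missing baseline with a conditional consequence. The AAQ-II, DBAS-10 and SHI have no value that treatment cannot have affected, and the stated reason for the timing fits only the CEQ. If session 1 has already moved ABC-SA scores favourably relative to control, change from the session 1 score understates the effect by the share f, and ANCOVA on it by about r×f. Neither f, D nor r is documented for these scales, and f may be zero.

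A reader might go further and infer that the trial's conclusions are weakened. They are not: no aim, hypothesis or power figure uses these scales. Nor does the gap invalidate the planned predictor analyses. Those run within the ABC-SA arm on baseline measures and do not name these scales, which are simply unavailable as baseline predictors. This is a cheap improvement to the process data.

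**What to change.** Give the AAQ-II, DBAS-10 and SHI with the Part 3 baseline questionnaires at Visit 3, before randomisation, and drop them from the end of session 1. Keep the CEQ at the end of session 1. Add the three scales to Table 5 and revise the timing sentence. State the analysis: session 6 score by randomised arm, adjusted for the Visit 3 value.

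For women already randomised without a Visit 3 score, label the session 1 score as post-randomisation and do not use it as a baseline covariate.

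Cost: 7 + 10 + 13 = 30 items move to a visit already planned at 60 to 90 minutes. The total for women who are treated does not change. Women who enrol but are not randomised would answer 30 extra items, and on the plan's figures they number 300 − 90 = 210. That falls to about 130 − 90 = 40 if the scales are limited to women whose WatchPAT result does not already rule out sleep apnea. This uses the plan's expected 130 with the condition and assumes that the recording is read before Visit 3.

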We have been studying sleep disorders among women Veterans since 2010,¹⁵ focusing on treatment preferences and adherence to psychological treatments for sleep disorders (e.g., cognitive-behavioral therapy for Insomnia; CBT-I). In treating insomnia, we found that the initial discomfort created by traditional CBT-I (e.g. sleep restriction therapy) may contribute to treatment discontinuation and non-adherence to recommendations among women Veterans. We therefore developed an insomnia intervention incorporating Acceptance and Commitment Therapy (ACT). ACT centers on mindfulness and focused choices consistent with a patient's values as reasons for implementing behavioral changes. ACT, which is currently being disseminated by VA as a treatment for depression and anxiety through an Evidence-Based Psychotherapy roll out, involves helping patients learn strategies for tolerating temporary discomfort in pursuit of values-based goals. We propose to use an ACT-based intervention to improve PAP adherence among women Veterans with SA.

The proposed study is a randomized controlled trial (RCT) to test the efficacy of an ACT-based program for improving PAP adherence called "ABC-SA" or "Acceptance and the Behavioral Changes to treat Sleep Apnea." This 6-session intervention differs from current approaches in two important ways. First, we will begin working on improving sleep quality before PAP therapy is initiated. Second, the ACT approach and techniques will address initial discomfort, link treatment to the patient's values and incorporate methods for accepting the behavioral changes required to treat SA (i.e. accepting and using PAP therapy). The main study outcomes will be assessed 3 months after PAP initiation, and PAP adherence will be monitored for 12 months. The 6-session "control" intervention will be modeled after "usual care" PAP education programs.

SPECIFIC AIMS

Aim 1: Test the efficacy of the ABC-SA program in improving PAP adherence, compared to a control program modeled after usual care, for women Veterans with SA.

Hypothesis 1a: Women who receive the ABC-SA program will show higher rates of PAP adherence (% of nights with \geq 4 hours of use) during the first 3 months of PAP use compared to those who receive the control program. Exploratory Hypothesis 1b: These effects will be sustained for up to 12 months.

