Aim 2: Test the efficacy of the ABC-SA program for improving objectively-measured and patientreported sleep quality, compared to the control program.

Hypothesis 2a: Women who receive the ABC-SA program will have better objectively-measured sleep quality at 3-months compared to those who receive the control program. Hypothesis 2b: Women who

receive the ABC-SA program will have better self-reported sleep quality at 3-months compared to those who receive the control program.

Exploratory Aim 3: Test the efficacy of the ABC-SA program for improving quality of life and symptoms of depression, compared to the control program.

Hypothesis 3a: Women who receive the ABC-SA program will demonstrate better quality of life at 3-months compared to those who receive the control program. Hypothesis 3b: Women who receive the ABC-SA program will demonstrate reduced symptoms of depression and fatigue at 3-months compared to those who receive the control program.

RESEARCH DESIGN AND METHODS

Basic Study Design (Figure 1)

The proposed study is a 4-year randomized controlled trial (RCT) to test the effectiveness of Acceptance and the Behavioral Changes to treat Sleep Apnea (ABC-SA), an ACT-based approach to improve PAP therapy adherence among women Veterans with SA. We anticipate enrolling 300 women to achieve the proposed sample of 90 randomized participants (45 ABC-SA and 45 controls).

Participants will complete a comprehensive sleep, mental health and physical health assessment at baseline (baseline), immediately after the intervention ends (post-treatment; approximately 1 month after PAP initiation), and 3 months after PAP initiation (primary endpoint). We will gather PAP adherence data for one year.

Primary outcomes will focus on differences in PAP adherence and patient-reported and objectively measured (wrist actigraphy) sleep quality at the 3-month follow-up. Data will be analyzed in an intention to treat analysis.

Setting The study will be carried out within VAGLAHS. In-person study assessments and intervention sessions will be completed at the Sepulveda Ambulatory Care Center (SACC) or West Los Angeles (WLA) campuses. Unattended sleep recordings (home sleep apnea testing; wrist actigraphy) will take place at participants' homes using study-provided equipment.

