Participants with stable psychiatric/medical conditions, and those using medications for sleep will not be excluded. Participants determined to be ineligible for the study will be notified by mail (see Participant Ineligibility Letter).

Randomization

Participants approved for randomization will be randomly assigned to the ABC-SA (n=45) or control program (n=45), following CONSORT guidelines.⁴⁷ Randomization sequences will be created using a computerized random number generator. Stratified randomization will help insure that groups (ABC-SA and control) are balanced in the severity of SA (AHI 5-15, and AHI>15). Furthermore, within each strata, the randomization sequences will be "blocked" using a block size of n=4. The study statistician will generate the stratified randomization sequence and transfer it to a series of "security envelopes". These envelopes, containing the group assignment, will be stored in a secure location that only authorized "unblinded" staff can access. This will assure random allocation concealment, which is critical to the integrity of randomized trials.

Study groups

• ABC-SA for women Veterans with SA (Table 4)

Participants randomized to ABC-SA group will receive the Acceptance and the Behavioral Changes to treat Sleep Apnea (ABC-SA) program that we developed to improve PAP adherence among women Veterans. The ABC-SA program melds strategies to improve sleep (stimulus control, targeted sleep hygiene, sleep compression) and increase PAP adherence (SA and PAP education) with psychological principles of ACT (e.g., using metaphors, linking behavior change to values, strategies for accepting discomfort). The program includes 6 weekly face-to-face meetings with the study interventionist, plus ongoing monitoring and support. Sessions are designed to last <45 minutes each. Issues specific to women's health are incorporated into ABC-SA, such as discussion of social factors that might impact PAP adherence (e.g., interpersonal relationships) and health issues among women (e.g., heart health, menopause and SA). Sessions are interactive to facilitate participant engagement. A written outline with the specific, individualized recommendations documented in clear language will be provided after each session. Interventionists will also complete session summaries for the participants to review at home.

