structure. Using the mixed-effects model, the difference in adherence rates between the ABC-SA and control groups will be assessed and tested at each month. To understand the nature of the treatment effects, we will dissect the "time by treatment" interaction into a series of tests of the simple effect of the treatment effect at each month. Figure 2 illustrates four possible patterns of results. Consistently significant treatment effects is consistent with Pattern 1. Significant treatment effects in early months, followed by non-significant effects in later months is consistent with Pattern 2. Nonsignificant treatment effects in early months, followed by significant treatment effects in the remaining months is consistent with Pattern 3. Lastly, finding significant treatment effects in the middle months, but not early and later months is consistent with Pattern 4.

Power Analysis: Power was computed assuming complete data (N=90; 45/group). Analyses focus on the treatment effect (ABC-SA vs. control) in terms of the proportion of nights with PAP use >4 hours per month; thus, the power analysis shows the power to detect differences in the proportion of nights of PAP use >4 hours per month between ABC-SA and control groups. The SD of this proportion is conservatively estimated as SD=.091 [computed as sqrt(.5*(1-.5)/30)=.0913]. Given this SD, alpha=.05 and power=.80, the study can detect a difference in the average proportion of nights of PAP use \geq 4 hours as small as 5.5% between ABC-SA and control for a given month. In interpreting the results, we will focus on larger, more clinically-important effects. This study will have ample power to detect clinically meaningful effects. The power to detect a 7.5% difference in adherence rates between groups would be .97. The power to detect a 20% difference would exceed .99. We would consider a difference of 10-15% to be clinically significant, and an effect >15% to be of substantial clinical importance. Results will be interpreted with these benchmarks in mind.

Aim 2 Data analysis/Sample Size Calculation: Aim 2 compares outcome measures that we expect to improve with improved PAP adherence. Outcomes tested are objectively measured (Aim 2a) and self-reported

(Aim 2b) sleep quality. The sample size for these analysis is expected to be N=72 (n=36 per group), accounting for 20% missing data from the 90 randomized participants.

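### The plan does not say which result decides Hypothesis 1a: the hypothesis covers the first 3 months of PAP use, the design text points to the 3-month follow-up, and the analysis tests each of 12 months.

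*Combined protocol and SAP*

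**What the plan says.** - **Window.** Specific Aims states Hypothesis 1a as higher adherence "during the first 3 months of PAP use compared to those who receive the control program". Exploratory Hypothesis 1b adds: "These effects will be sustained for up to 12 months".
- **Time point.** The Introduction says "The main study outcomes will be assessed 3 months after PAP initiation". Basic Study Design labels the assessment "3 months after PAP initiation (primary endpoint") and adds: "Primary outcomes will focus on differences in PAP adherence and patient-reported and objectively measured (wrist actigraphy) sleep quality at the 3-month follow-up".
- **Outcome unit.** PAP devices: "We will use monthly PAP use as an outcome measurement". The Aim 1 section defines 12 consecutive 30-day periods, and 12-month PAP monitoring runs them from PAP initiation.
- **Analysis.** One 2x12 mixed model (group by categorical month) serves both 1a and 1b. The group difference is tested at every month: "we will dissect the 'time by treatment' interaction into a series of tests of the simple effect of the treatment effect at each month". Four patterns of significant and non-significant months are then described.
- **Alpha, power and benchmarks.** Study Design Considerations sets two-tailed alpha of .05 for all significance tests. The Aim 1 power analysis is for one unspecified month. It calls a 10-15% difference clinically significant and more than 15% of substantial clinical importance.
- **Randomisation.** "Stratified randomization will help insure that groups (ABC-SA and control) are balanced in the severity of SA", with strata AHI 5-15 and AHI above 15. The stated mixed model and ANCOVAs do not include the stratum.

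**The concern.** Hypothesis 1a is one claim about a window, but the analysis yields twelve monthly results and no rule turns them into an answer. It could be read as a months 1-3 average, month 3 alone, or any or all of months 1-3. The interaction cannot be the test, because a constant benefit in every month (the plan's Pattern 1) produces no interaction. The 12-month main effect covers a wider window than 1a.

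Two analysts could therefore take the same data and reach opposite answers on the main hypothesis, with the choice made after seeing the results.

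For 1b, the plan describes durability by which months reach significance. A significant month followed by a non-significant one is not evidence that the effect changed.

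**Working it through.** **1. The plan's own power figure.** Inputs from the Aim 1 Power Analysis: 45 per group, SD = sqrt(.5 x .5/30) = .0913, two-sided .05, power .80. The SE is .0913 x sqrt(2/45) = .0192. The detectable difference is (1.960 + .842) x .0192 = .054 (normal), or .0545 with t on 88 df. This agrees with the stated 5.5%. Power at 7.5% is .97, as stated. The figure reproduces, but it belongs to a single unnamed month.

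**2. What each possible rule for 1a would do.** The documents give no between-month correlation and no between-woman SD. The following are therefore assumptions: normal data, 45 per arm, exchangeable correlation .6 to .9, and effects set by power per month instead of percentage points. The noncentrality per month is d x sqrt(45/2), so d = .597 gives 2.83, which is 80% power. There were 40,000 simulated trials per cell, with t tests on 88 df.

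| Rule for 1a | Alpha, no effect | Power when each month has 80% |
|---|---|---|
| Month 3 alone | .05 | .80 |
| Any of months 1-3 | .084-.119 | .87-.94 |
| All of months 1-3 | .005-.022 | .63-.72 |
| Months 1-3 averaged, one contrast | .048-.051 | .83-.90 |

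The last row can be checked by hand. Averaging three months multiplies the SD by sqrt((1 + 2r)/3), which is .856 at r = .6 and .966 at r = .9. The noncentrality becomes 2.83/.856 = 3.31 or 2.83/.966 = 2.93, giving power of about .91 and .83.

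Months 1-3 disagree (some significant, some not) in 15-30% of trials at 80% power per month, 10-18% at 90% and 6-10% at 95%. In those trials the answer to 1a depends on the rule.

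**3. Exploratory 1b with a constant effect, 80% power per month.**
- Months 1-3 all significant and at least one of the nine later months not: 9-22% of trials (exchangeable correlation).
- Months 1-3 all significant and most later months not, which is closer to Pattern 2: about 1% under exchangeable correlation and 5% under AR(1).
- A focused contrast (months 4-12 mean difference minus months 1-3 mean difference) and the 11-df interaction each reject in about 5%, as they should.
- If the effect truly halves after month 3 (90% power per month early), the focused contrast detects it in 97% of trials and the interaction in 74% at correlation .6. Both reach about 100% at .9.

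**4. Stratum.** If it explains 5-10% of outcome variance (assumption), the unadjusted SE is too wide by 1/sqrt(.95) = 1.026 to 1/sqrt(.90) = 1.054. True alpha is 2 x (1 - Phi(1.96 x 1.026)) = .044, falling to .039.

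**5. Visit anchor.** Basic Study Design puts the visit 3 months after PAP initiation, whereas Three-month follow-up puts it 3 months after session 6. Post-treatment assessment starts at session 6, which Basic Study Design places about 1 month after PAP initiation. The second anchor is therefore about 1 + 3 = 4 months after initiation.

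**The case against.** The best reply is that a month-3 test is already implied. Three months after PAP initiation is labelled the primary endpoint, monthly use is the outcome, each month is tested, alpha is .05 and power is given for a month. That reading is coherent, with defined alpha and power. It stands as one of two readings, but it does not settle the matter, because Hypothesis 1a itself speaks of the whole first 3 months and the power statement names no month.

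It is also fair that the plan does not rest on significance alone, since it promises to read results against clinical benchmarks. These do not say which month or average they apply to. Hypothesis 1b is labelled exploratory, and its patterns are offered as illustrations.

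Three stronger inferences are tempting and not supported:
- **That the plan inflates the type I error.** With independent tests, any of 12 months would give 1 - .95^12 = 46%. No section says that any significant month counts as success, and repeated months on the same women are not independent. The any-of-months-1-3 rule is likewise hypothetical, and .05 per month is itself read from the blanket statement.
- **That 9-22% of constant effects would be classified as fading.** That rate counts a single non-significant later month, which is not Pattern 2.
- **That omitting the stratum endangers the conclusions.** The omission is conservative.

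**Conclusion.** The point holds as an unreconciled specification and should be corrected before adherence is compared by arm. The documents support a months 1-3 reading and a month-3 reading of Hypothesis 1a and do not choose between them. Neither the existence of the gap nor the case for closing it depends on the simulations. Their sizes do depend on the assumed correlations (.6-.9) and per-month power. Within that range, the choice of rule matters in roughly 15-30% of trials at 80% power per month, and less if power is higher.

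For 1b the weakness is one of method: the pattern reading does not estimate change. The rate of outright misclassification as Pattern 2 is low.

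The stratum is a small gain in precision. The visit-anchor conflict is a separate matter that mainly affects the timing of the Aim 2 and 3 assessments, because the 30-day adherence periods run from PAP initiation. It would touch 1a only if adherence at the 3-month follow-up were taken to mean data up to the visit date.

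**What to change.** 1. In the same mixed model, pre-specify the ABC-SA minus control difference averaged over months 1-3 from PAP initiation, two-sided .05, as the single test of Hypothesis 1a, and align Basic Study Design with it. A single pre-specified month-3 test would also close the gap. The average is preferable because it matches the hypothesis as worded and has at least the power of a single month under the assumptions above.
2. Report the monthly differences as estimates with confidence intervals, read against the stated benchmarks, and say which quantity the benchmarks apply to.
3. For 1b, estimate the months 4-12 average difference and its change from the months 1-3 average, with confidence intervals, in place of sorting by significance pattern.
4. Add the AHI stratum (5-15, above 15) as a fixed effect in the mixed model and in the Aim 2 and 3 ANCOVAs.
5. Separately, reconcile the two anchors for the 3-month visit.

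Items 1-4 need only changes of wording in the analysis plan. They use the same data and the same model, and the stratum costs one degree of freedom.
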